**SECTION 3: PARTICIPANTS AND RECRUITMENT**

**3.1 Who will be the participants in this project?**

Participants also includes data about people or human tissue samples.

There will be three groups in this study:

- 1.Existing patients who have received treatment for POTS in accordance with established clinical guidelines who meet eligibility criteria will be enrolled;
- 2.Patients who have previously documented SARS-CoV-2 infection with subsequent unexplained chronic illness greater than 3 months will be recruited through Long Covid support groups on social media sites;
- 3.Healthy controls, age and gender matched

**3.2 Does the planned or anticipated recruitment of participants target, focus on, or include as a group, any of the following population groups? Select as many as relevant.**

This question is to capture the planned or foreseeable recruitment of participants from these population groups, rather than their incidental inclusion. Select as many groups as applicable to the research.

Participant group		Participant group	
Aboriginal and Torres Strait Islander people		People who may be involved in illegal activities	

Children and young people		People with a cognitive impairment, an intellectual disability or a mental illness	
Defence Force personnel		Primary or secondary school students	
People highly dependent on medical care who may be unable to give consent		University students	
People in dependent or unequal relationships		Women who are pregnant and the human fetus	
People in other countries		None of these participant groups	X

### 3.3 What is the number of participants?

Cohort One (LCS): 150 consecutive patients with LCS will be recruited from various social media and LCS support group platforms.

Cohort Two (POTS) 34 consecutive patients with POTS will be recruited from a speciality POTS clinic run by [name] who is an Assoc/Prof at The University of Adelaide, Centre for Heart Rhythm Disorders

Cohort Three (Controls): 34 healthy, matched age and gender controls will be recruited from University and private medical campuses.

A base sample size calculation can be made using the formula:  $n = (t^2 \times p(1-p)) / m^2$ , where  $t$ =confidence level at 95%,  $p$ =estimated prevalence of POTS within an LCS sample and  $m$  is the relative precision. Using this formula, a sample size of 139 provides sufficient statistical power to estimate a proportion (10% POTS amongst LCS) with a precision of 5% at the 95% confidence level. The number is increased to 150 to allow for withdrawal from the study.

From Walker et al. 2013 paper, the following information was obtained: at 30 minutes of orthostatic time, Stand healthy group (N=15) had mean orthostatic change in heart rate 26 bpm + SE=4 (SD=SE\*SQRT(N) = 15.5) and the Stand POTS group (N=15) had mean orthostatic change in heart rate 45 bpm + SE=5 (SD=SE\*SQRT(N) = 19.4). Using a two-sample Satterthwaite t Test assuming unequal variance, with alpha=0.05, two-sided test and SD=15.5 and 19.4, it was found that there was 80% power to detect a mean difference of 45-26=19 when using a sample size of N=15 per group. If there is expected to be 20% loss to follow up, then a total of  $(20/9)*30=66.66$  so N=34 is required in each group (N=68 in total) The statistical software used was SAS 9.4 (SAS Institute Inc., Cary, NC, USA).

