## SECTION 2: NATURE OF THE PROJECT

### 2.1 Aims of the project:

Discuss in standard English the main research aims/hypotheses to be investigated.

The primary objective of this study is to:

[1] Assess the prevalence of POTS in those with LCS, using a standardised and detailed autonomic testing protocol

The secondary objectives of this study include:

[2] Characterising the neuroendocrine/inflammatory/immune biomarker profile of those with LCS(+)/POTS/LCS(-)/POTS and POTS and compare to matched, healthy controls

[3] Determining the impact of LCS with and without POTS and POTS on quality of life & symptom scores, cognitive function and psychological well-being and compare to matched, healthy controls

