## 2.6 Location(s) of the research:

Include details of all sites where the project will be undertaken and locations of participants.

Participant assessments will be undertaken by the Centre for Heart Rhythm Disorders (CHRD) at two sites. The first site is in Norwood, South Australia and the other Cardiovascular Services in Kew East, Melbourne, Victoria. Additionally, controls can undergo their autonomic testing in the clinical rooms at the UoA/SAHMRI, North Tce, Adelaide. This facility provides a clinical setting that is appropriate to the research and allows for added convenience for students who wish to volunteer for the research. No patients will be recruited from public health organisations and no data collection will take place at public health spaces. Due to the scarcity of specialists treating dysautonomia in Australia, many patients access care from interstate via telehealth or interstate visits to the Adelaide clinic. Use of private rooms in Melbourne will facilitate higher enrolment and study participation rates. As Victoria, Australia had one of the largest SARS-CoV-2 infection rates in Australia, it is supposed that there will be higher rates of LCS in this state. All study investigators have appropriate Australian professional registration and indemnity which will cover patient/clinician interaction in both states.

All studies will be undertaken in a quiet, dimly lit room with a comfortable ambient temperature between 21-24 degrees Celsius.

**2.7 If research is to be conducted with or about participants living outside Australia outline any local legislation, regulations, permissions or customs that need to be addressed before the research can commence. Outline the steps taken to ensure that this has been adequately considered and addressed.**

See *National Statement Chapter 4.8*. Attach authorising correspondence and/or approval documentation to the application. If you are travelling to a region classified as level 3 or 4 according to the [Department of Foreign Affairs and Trade](#), travel approval may be required. See The University of Adelaide's [travel safety information in the HSW Policy and Handbook](#).

n/a

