### 3.4 What is the age range of participants?

>18 years old. Controls will be matched to age and gender of the POTS and LCS cohorts

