### **3.7 Where will participants be recruited or sourced from?**

Any use of snowball sampling for recruitment should only be in the passive form. That is participants may be asked to discuss the research with friends/contacts who they think may be interested in volunteering to be participants. Those new participants should then contact the research team to volunteer.

Participants will be recruited through social media forums that pertain to support of those with LCS. Administrators of social media platforms for LCS will be approached by senior investigators for permission to post information about the study with contact details for researchers. We recognised the selection bias associated with this method of recruitment, however given the extraordinary nature of the current pandemic and the lack of understanding of LCS and its associated diagnosis and aetiology, it would seem that this bias is justified by the urgent requirement for preliminary understanding of the condition. As this study looks to explore immune, inflammatory and cardiovascular changes rather than efficacy of interventions, the use of convenience sample is more tolerable.

In addition, consecutive patients with POTS who attend [name] practice and The University of Adelaide, Centre for Heart Rhythm Disorders will be recruited. Potential participants may be approached by a member of the clinic/study staff via email introducing the study and providing the plain language patient information sheet explaining the purpose of the study. Healthy controls will be recruited through flyers and posters placed within The University of Adelaide health and education campuses. In addition, healthy controls referred to CHRDC/CVC for investigation of heart arrhythmia (but found to have none) will be recruited via the above mentioned flyers. Advertisements will be placed on the SAHMRI and University of Adelaide facebook sites as per attachment 5.

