### Study Day Testing

1. Physical assessment including vital signs, height, weight and BMI. 5 minutes
2. Valsalva manoeuvre is used to assess normal or disordered autonomic control of blood pressure and heart rate. The test requires the maintenance of forced expiration against resistance for 15 seconds and beat to beat, non-invasive blood pressure and heart rate monitoring. 5 minutes
3. Deep breathing test requires the subject to breathe at 6 breaths per minute while undergoing non-invasive 'beat to beat' blood pressure and heart rate monitoring to determine cardiovascular function. 10 minutes
4. Sudomotor function testing requires the subject to place hands and feet on SUDOSCAN metal plates. Reverse iontophoresis and chronoamperometry are used to assess chloride ion concentration of the skin which represents a measure of sudomotor output. This test is painless and non-invasive and requires the subject to stand still for 3 minutes while the SUDOSCAN assesses function. 5 minutes
5. Orthostatic challenge requires the subject to lay supine while 'beat to beat' non-invasive BP and HR recordings are taken. The subject then stands still for 10 minutes and changes in BP and HR are monitored. 12 minutes
6. Blood Draw: Subjects will undergo standing blood draw of 15 ml (3 teaspoons).
7. CANTAB cognitive testing requires the participant to complete a series of neurocognitive tests (CANTAB: Cambridge Neuropsychological Test Automated Battery, Cambridge Cognition Ltd.) to assess executive function, reaction time, memory, and attention. This testing is undertaken in the seated position, using an IPAD. The assessment time is approximately 30 minutes and includes the following tests:
  - Memory:  
Delayed Matching to Sample which assesses visual matching ability and short-term visual recognition memory.
  - Executive Function:  
Multi-tasking Test which assesses the subject's ability to manage conflicting information and to ignore task-irrelevant information.
  - Attention and Psychomotor Speed:  
Reaction Time: which assesses motor and mental response speeds, as well as measures of movement time, response accuracy, reaction time, and impulsivity.

Rapid Visual Information Processing which is a measure of sustained attention

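### Controls are matched on age and gender only and education is not a named variable, so the CANTAB comparison, chiefly Long COVID against controls, is open to confounding by education

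*Protocol*

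**What the plan says.** Protocol section 2.1 lists, within secondary objective 3, the effect of LCS and POTS on "cognitive function and psychological well-being and compare to matched, healthy controls". Section 3.16 (Study Day Testing) specifies a CANTAB battery "to assess executive function, reaction time, memory, and attention", and the testing table in section 2.5 applies it to all three cohorts.

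On where the groups come from:

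- **Controls.** Section 3.3: "34 healthy, matched age and gender controls will be recruited from University and private medical campuses". Section 3.7: "Healthy controls will be recruited through flyers and posters placed within The University of Adelaide health and education campuses". Sections 3.7 and 3.8 add university and research-institute Facebook pages and practice flyers, and "healthy controls referred to CHRDC/CVC for investigation of heart arrhythmia (but found to have none) will be recruited via the above mentioned flyers". Section 2.6 offers a campus testing room that "allows for added convenience for students who wish to volunteer for the research".
- **LCS.** Section 3.3: "150 consecutive patients with LCS will be recruited from various social media and LCS support group platforms".
- **POTS.** Sections 3.3 and 3.7 name a specialty clinic. Section 3.8 adds university social media, practice internet advertisements, and practice and university flyers.

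On matching, section 3.4 says: "Controls will be matched to age and gender of the POTS and LCS cohorts". Sections 3.1 and 3.3 name the same two variables. No section names education as an eligibility, matching, recorded or adjustment variable. A demographic survey goes to every cohort (sections 2.5 and 3.16), but its items are not shown. For controls, its stated purpose is to check eligibility.

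**The concern.** Memory, attention and executive-function scores may differ with education for reasons unrelated to disease. Controls who respond to notices on campuses, at a research institute and at a private practice may differ in education from people who respond through LCS support groups. Matching on age and gender does nothing about that. If the groups differ, part of any cognitive difference credited to LCS would be a difference in who was recruited.

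The comparison leans heavily on these 34 controls. The CANTAB pages attached to the protocol advise against replacing a control group with normative data, so norms are not an easy fallback. Section 3.7 does discuss selection bias, but only for LCS recruitment. It defends the convenience sample by pointing to immune, inflammatory and cardiovascular outcomes, and does not mention cognition or the choice of controls.

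This is more than an analysis detail left for later. Recruitment sources and matching variables are fixed in this protocol, and no later analysis can adjust for a variable that was not collected.

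**Working it through.** **The plan's own figures.** There is none for cognition. The 34 per group in section 3.3 starts from orthostatic heart-rate change: difference 19 bpm, SDs 15.5 and 19.4, 15 per group. By the noncentral t with Satterthwaite degrees of freedom I get 81.5% power at 15 per group, against the stated 80%. That figure says nothing about CANTAB scores. The cognitive illustration below is mine.

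**Inputs from the protocol.** 150 LCS, 34 POTS and 34 controls (section 3.3); two-sided test at 0.05 (section 5.5).

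**Assumed inputs.** Let g be the education gap between controls and patients in SD units, and r the correlation of education with test score. The shift in mean score due to education alone is b = g × r, in SD units. The documents give neither value. Examples:

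- g = 0, any r: b = 0
- g = 0.5, r = 0.2: b = 0.10
- g = 0.8, r = 0.3: b = 0.24
- g = 1.0, r = 0.2: b = 0.20
- g = 1.0, r = 0.3: b = 0.30

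A negative g reverses the sign. The two-sided rejection rate is then the same, but the bias hides a deficit instead of inflating one.

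**Formula.** With no disease effect, a two-sample t test has noncentrality b / √(1/n₁ + 1/n₂) on n₁ + n₂ − 2 degrees of freedom. For 150 v 34, √(1/150 + 1/34) = √0.03608 = 0.1899, with 182 degrees of freedom. At b = 0.2 the noncentrality is 0.2 / 0.1899 = 1.05.

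**Chance of rejecting with no disease effect:**

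| Shift b (SD) | 150 LCS v 34 controls | 139 v 27 | 34 POTS v 34 controls |
|---|---|---|---|
| 0 | 5.0% | 5.0% | 5.0% |
| 0.1 | 8.2% | 7.6% | 6.9% |
| 0.2 | 18.2% | 15.7% | 12.8% |
| 0.3 | 34.9% | 29.4% | 23.0% |

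The middle column uses the 139 that section 3.3 derives before its withdrawal allowance, and 34 × 0.8 = 27 controls after the plan's 20% loss. The conclusion does not depend on which counts are used. The POTS column is shown only for the same shifts. Shared recruitment channels make a given gap less plausible there.

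**Scale.** With 150 v 34, the smallest difference detectable at 80% power is about 2.80 × 0.1899 = 0.53 SD. A shift of 0.2 to 0.3 SD is roughly 40% to 55% of that (0.2/0.53 and 0.3/0.53).

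**The case against.** The strongest reply is that nothing in the protocol shows the groups differ in education. Support-group volunteers are self-selected, and POTS patients attend private specialist rooms; neither fact implies less schooling. Some controls are cardiology referrals or Facebook responders, and no proportions are given. POTS patients see university flyers and social media too. The CANTAB tasks range from reaction time to non-verbal pattern matching, so a single correlation with education need not fit all of them. At a shift of 0.1 SD the rejection rate is 8%, not far above nominal. All of this stands, and it limits the point to exposure to bias.

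Three stronger readings are tempting, and the documents support none of them:

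- **That the controls will be better educated and the deficit overstated.** There are no education data for any cohort, so the direction is unknown.
- **That the control group will be mostly students, contradicting section 3.2.** Section 2.6 only mentions convenience for students who volunteer. The section 3.2 tick-box excludes incidental inclusion, and age matching limits how many young students can enter.
- **That the protocol commits to unadjusted tests of CANTAB scores.** Section 5.5 gives summaries for continuous variables and chi-square or Fisher tests for categorical ones. It fixes no test for these scores, and an analysis plan not shown here could specify an adjusted model.

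The demographic survey may also already ask about education. That would supply the data, but the protocol does not say so.

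**Conclusion.** The point holds as an exposure left open by the design. For a named cognitive objective, the protocol fixes different recruitment channels for LCS and controls and matches on age and gender only. It does not commit to recording education. The LCS-control contrast is the one chiefly affected, and the POTS-control contrast less so. The primary prevalence estimate uses no controls. The contrast of LCS with and without POTS draws both groups from one source, so it does not carry this particular weakness.

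The size cannot be established from the documents. Under assumed shifts of 0 to 0.3 SD, the false-positive rate for 150 v 34 runs from 5% to 35%, and a gap in the opposite direction would mask a true deficit. These figures illustrate sensitivity and do not predict what the study will find. Because the objective is secondary and the remedy is cheap, the change is worth making but is not critical to the study.

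**What to change.** Before recruitment, confirm that the demographic survey in sections 2.5 and 3.16 records highest education level or years of education in all three cohorts, including controls, and add the item if it does not. Report its distribution by cohort. Compare each CANTAB outcome with controls by a regression adjusted for age, gender and education.

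Balancing the controls on education at group level, where feasible, is optional. It would help if the cohorts turned out to overlap little, because adjustment would then rest on extrapolation. A fixed cap on students or health professionals is not needed.

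The cost is one survey item and one covariate. The adjusted deficit may be smaller, or estimated slightly less precisely.

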### **Inclusion Criteria**

Cohort 1 (LCS): Adults aged  $\geq 18$  years old (male or female); Able to provide written informed consent; previous SARS-CoV-2 infection (As some Australians contracted SARS-CoV-2 in countries that did not undertake testing in the early stages of the pandemic, some participants will not have a diagnosis by PCR. Inclusion with physician confirmed Long Covid is consistent with worldwide research practices for Long Covid studies); continuing chronic symptoms persisting for  $\geq 3$  months post-acute COVID-19 infection and not attributable to an alternative disease state.

Cohort 2 (POTS): Adults aged  $\geq 18$  years old (male or female); POTS diagnosis; Able to provide written informed consent; Diagnostic criteria for POTS met as per the following: 1. sustained heart rate elevation of  $\geq 30$  beats/min within 10 minutes. 2. No other secondary cause of these symptoms. 3. Absence of orthostatic hypotension 4. Symptomatology present for greater than 3 months

Cohort 3 (Healthy Control): Otherwise, healthy adults aged  $\geq 18$  years old (male or female); Able to provide written informed consent; absence of POTS diagnosis or previous SARS-CoV-2 infection.

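### The only power statement for the POTS and control cohorts rests on heart-rate change at 30 minutes of standing, so it does not support secondary objectives [2] and [3]

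*Protocol*

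**What the plan says.** Section 3.3 gives two calculations. The first sizes the LCS cohort for the primary objective: 139 people for a prevalence of 10% with 5% precision, raised to 150.

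The second concerns the POTS and control cohorts. It takes from a published comparison that "at 30 minutes of orthostatic time, Stand healthy group (N=15) had mean orthostatic change in heart rate 26 bpm" and that "the Stand POTS group (N=15) had mean orthostatic change in heart rate 45 bpm". The test and inputs are given as "Using a two-sample Satterthwaite t Test assuming unequal variance, with alpha=0.05", "two-sided test and SD=15.5 and 19.4", and the result is that "there was 80% power to detect a mean difference of 45-26=19 when using a sample size of N=15 per group". The text then moves to 34 per group, citing 20% loss to follow-up.

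Three other places bear on this:
- Study Day Testing (section 3.16), orthostatic challenge: "The subject then stands still for 10 minutes and changes in BP and HR are monitored". Twelve minutes are allotted to the whole item.
- Inclusion Criteria (section 3.6), Cohort 2: entry requires a "sustained heart rate elevation of" at least 30 beats/min within 10 minutes. Controls must have no POTS diagnosis.
- Aims (section 2.1): objective [1] is the prevalence of POTS in LCS. Objective [2] is "Characterising the neuroendocrine/inflammatory/immune biomarker profile of those with" LCS with POTS, LCS without POTS, and POTS, compared with matched healthy controls. Objective [3] makes the same group comparisons for quality of life, symptom scores, cognition and psychological well-being.

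**The concern.** A power statement is useful when its endpoint is one the study observes and intends to test. This one falls short in three ways. The planning values belong to a 30-minute stand and the study uses a 10-minute stand, for which no means or SDs are given. The POTS group is chosen for a large orthostatic heart-rate rise, so a difference from controls in that variable is largely settled at enrolment. And no objective asks whether heart-rate change differs between POTS patients and controls.

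The POTS and control cohorts exist for objectives [2] and [3]. Section 5.5 applies a two-sided threshold of 0.05 to all tests. With 80% as the only power figure for these cohorts, a non-significant antibody, cytokine or SF-36 comparison could be read as coming from an adequately powered design, although the 80% belongs to a large effect on a different variable.

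**Working it through.** **1. Reproducing the stated power.** Inputs from section 3.3: means 45 and 26 bpm, standard errors 5 and 4, 15 per group, two-sided alpha 0.05.
- SDs: 4 × √15 = 15.5 and 5 × √15 = 19.4, as stated.
- Standard error of the difference: √(15.5²/15 + 19.4²/15) = √(16.02 + 25.09) = 6.41.
- Noncentrality: 19/6.41 = 2.96. Satterthwaite degrees of freedom: 26.7.
- Power from the noncentral t distribution: 81.5%. With 14 per group it is 78.5%, so 15 is the smallest size reaching 80%.
- Standardised effect assumed: 19/√((15.5² + 19.4²)/2) = 19/17.56 = 1.08.

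The arithmetic of the power statement is sound.

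**2. Endpoint against design.**

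| | Power statement (3.3) | Study as designed |
|---|---|---|
| Time on standing | 30 minutes | 10 minutes (3.16) |
| Role of heart-rate rise in POTS | outcome | entry criterion, within 10 minutes (3.6) |
| Comparison | heart-rate change, POTS v healthy | biomarkers, quality of life, symptoms, cognition, well-being (2.1) |

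No 30-minute orthostatic reading is described in the text. The schema figure is not shown, but the 12 minutes allotted to the test leave no room for one.

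**3. What the planned numbers deliver for [2] and [3].** The protocol gives no effect size for these outcomes, so only detectable standardised differences can be computed. Method: two-sample t test, n1 + n2 − 2 degrees of freedom, noncentrality d × √(n1·n2/(n1 + n2)), solved for 80% power at two-sided 5%, without multiplicity adjustment.

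Group sizes: 34 per group as planned; 34 × 0.8 = 27.2, taken as 27, after 20% loss; LCS split at the protocol's 10% (15 with POTS, 135 without). Because prevalence is what the study sets out to estimate, 20% (30 with POTS) and 30% (45 with POTS) are added as assumptions.

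| Comparison | n | Detectable d |
|---|---|---|
| POTS v controls | 34 v 34 | 0.69 |
| POTS v controls, after 20% loss | 27 v 27 | 0.78 |
| LCS without POTS v controls (10% prevalence) | 135 v 34 | 0.54 |
| LCS with POTS v controls, 10% | 15 v 34 | 0.89 |
| LCS with POTS v controls, 20% | 30 v 34 | 0.71 |
| LCS with POTS v controls, 30% | 45 v 34 | 0.65 |

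For illustration only, since d = 0.5 has no source in the protocol, power at that difference is 53% (34 v 34), 44% (27 v 27), 74% (135 v 34) and 35% (15 v 34).

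**The case against.** Several points on the other side are fair.

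- A reader might infer that the study never measures the power endpoint at all. That goes too far. Orthostatic heart-rate change is recorded in all three cohorts; it is the 30-minute value that is not. Nothing in the documents shows that 10-minute values would give a different sample size.
- A reader might also infer that the sample size supports none of the objectives. The documents do not bear this out. Objective [1] has its own precision calculation, which reproduces: 1.96² × 0.1 × 0.9/0.05² = 138.3, rounded up to 139.
- Section 3.3 ties its 80% explicitly to heart rate and claims no power for other outcomes. The protocol elsewhere describes its biomarker work as exploratory, and a protocol need not state a detectable difference for every secondary outcome. This stands, and the absence of such figures is not the fault alleged. The fault is that the justification the protocol does give rests on an endpoint that does not fit its design. The likelihood of misreading is a judgement.
- On the protocol's own endpoint the cohorts are not short: power is about 99% at 34 per group and 97% at 27. That is true, but it is surplus for a comparison that is not an objective.
- The 19 bpm difference leads to 15 per group, not 34. The further step to 34 does not follow from 20% loss either: 30/0.8 = 37.5, so 38 in total or 19 per group. This is a separate matter in the same paragraph, and it means that removing the heart-rate calculation takes away little of what actually produced 34.

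**Conclusion.** The point holds for the POTS and control cohorts and secondary objectives [2] and [3]. Their only power statement is computed correctly, but for a 30-minute reading that the 10-minute test does not provide, on the variable that defines one of the two groups, in a comparison that is not an objective. The assumed effect of 1.08 carries no information about biomarkers, questionnaires or cognitive scores. For those, the planned numbers reach 80% power only at about 0.54 to 0.89, depending on the comparison and on POTS prevalence in LCS.

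These figures assume roughly normal outcomes with equal variances, the group sizes shown, and each test at a nominal 5%. Multiplicity adjustment would raise them. Only the 27 v 27 figure allows for loss. It does not follow that the cohorts are too small: the protocol names no difference worth detecting for these outcomes, so adequacy cannot be judged either way. The primary prevalence estimate is unaffected.

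**What to change.** In section 3.3, remove the 30-minute heart-rate calculation as the justification for 34 per group, keep the sample, and state what it delivers for [2] and [3]. Suggested content: at 80% power and a two-sided nominal 5% level, unadjusted for multiplicity, the study can detect standardised differences of about 0.69 for POTS versus controls (0.78 if 27 per group remain after 20% loss), about 0.54 for LCS without POTS versus controls (135 v 34), and for LCS with POTS versus controls about 0.89, 0.71 or 0.65 if prevalence is 10%, 20% or 30%. Add that a null result does not exclude smaller differences.

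The cost is one rewritten paragraph and a less favourable stated capability. No participants are added and no procedure changes.

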**2.5 Research methodology:**

Describe how the study will be undertaken and explain what interactions will occur between researchers and participants. Include a description of the research methodology and how this will achieve the research aims. For example, you could include a justification of why the sample size/sampling method will yield valid and reliable results. Where appropriate, please refer back to the aims described in 2.1 when describing the methodological approach.

We plan to enrol 218 participants for this study (n= 150 with LCS, n=34 with POTS, n = 34 healthy matched controls). Subjects who meet the inclusion and none of the exclusion criteria and who provide informed consent, will be invited to attend in person to facilitate physical examination including autonomic testing, blood draw and associated investigations (see table below). The comprehensive nature of this exercise will allow subjects to complete various tools/questionnaires at their leisure via online portal links to a secure REDCap database, to reduce the impact of fatigue on the accuracy of findings.

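### Section 3.3: 15 per group with a 20% loss gives 19 per group, not the 34 called required; base size, loss rate and inflation factor need reconciling

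*Protocol*

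**What the plan says.** Section 3.3 contains two separate calculations.

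- **POTS and control groups.** Means and standard errors for the orthostatic heart-rate change come from a published standing study with 15 people per group. The standard errors are converted to standard deviations of 15.5 (healthy) and 19.4 (POTS). The test is described as "Using a two-sample Satterthwaite t Test assuming unequal variance", "with alpha=0.05, two-sided test and SD=15.5 and 19.4", and the result is "80% power to detect a mean difference of 45-26=19 when using a sample size of N=15 per group". The next sentence begins "If there is expected to be 20% loss to follow up", computes 20/9 times 30 as 66.66, and ends "so N=34 is required in each group (N=68 in total").
- **LCS cohort.** A separate precision formula gives 139 for a 10% prevalence estimated to within 5 points at 95% confidence. Then: "The number is increased to 150 to allow for withdrawal from the study". No withdrawal rate is given.

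Section 2.5 carries the results forward: "We plan to enrol 218 participants for this study", made up of 150 with LCS, 34 with POTS and 34 controls.

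**The concern.** The base size, the loss rate and the resulting group size are stated together, and the third does not follow from the first two. A 20% loss calls for a multiplier of 1/0.8 = 1.25. The text uses 20/9 = 2.22. No other passage corrects or explains this.

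The form in section 2.5 invites a justification of the sample size, and section 3.3 presents 34 as a requirement. That figure supplies 68 of the 218 planned participants. An ethics committee reading 3.3 would take it that 68 people are needed for the stated comparison, when the stated assumptions give 38. Some of the POTS participants would also stop the medications listed in section 2.5 for the testing day, so the number is not purely administrative.

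**Working it through.** **Inputs, all from section 3.3:** difference 45 − 26 = 19 bpm; SDs 15.5 and 19.4; two-sided alpha 0.05; unequal-variance t test; 15 per group; loss 20%; factor 20/9; result 34 per group (68 in total). For LCS: prevalence 10%, precision 5 points, 95% confidence, 139 raised to 150.

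**1. The base size reproduces.**
- SDs: 4 × √15 = 15.5 and 5 × √15 = 19.4.
- Standard error of the difference at 15 per group: √[(15.5² + 19.4²)/15] = √(616.61/15) = 6.41.
- Noncentrality: 19/6.41 = 2.96, with about 26.7 Satterthwaite degrees of freedom.
- Power from the noncentral t distribution: 81.5% (simulation 81.3%). At 14 per group it is 78.5%, so 15 is the smallest size that reaches 80%.

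**2. The loss step does not reproduce.**
- Dividing by the retained fraction: 30/(1 − 0.20) = 37.5; per group 15/0.8 = 18.75, so 19 per group and 38 in total.
- The looser convention N × (1 + d): 15 × 1.2 = 18 per group, 36 in total.
- Neither gives 34.

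**3. What 20/9 corresponds to.**
- (20/9) × 30 = 66.67, so the multiplication itself is right.
- 20/9 is the reciprocal of 0.45, which means 45% retained and 55% lost. After rounding up to 34, 1 − 15/34 = 55.9%.
- The same product is 60/0.9 = 66.67, which is 30 per group with a 10% loss (33.3, rounded up to 34). That route reaches 34 but contradicts both the stated 15 per group and the stated 20%.
- 30 per group with a 20% loss would be 30/0.8 = 37.5, so 38 per group.

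**4. What 34 per group delivers for 19 bpm.**

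| Evaluable per group | How reached | Power |
|---|---|---|
| 15 | base size; also 19 enrolled less 20% (15.2) | 81.5% |
| 19 | 19 enrolled, no loss | 90.0% |
| 27 | 34 enrolled less 20% (27.2) | 97.4% |
| 34 | 34 enrolled, no loss | 99.3% |

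**5. LCS cohort (side note).**
- Base: 1.96² × 0.1 × 0.9/0.05² = 138.3, so 139. This reproduces.
- Loss covered by 150: 1 − 139/150 = 7.3% (as an increase in n, 150/139 − 1 = 7.9%).
- If 20% were lost here too: 150 × 0.8 = 120, with half-width 1.96 × √(0.09/120) = 0.0537, about 5.4 points.

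**The case against.** **The error is in the safe direction.** It yields more participants and more power than stated for the heart-rate comparison, and the primary objective, POTS prevalence in LCS, is sized separately. This stands, and it sets the severity.

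**A larger group may be wanted anyway.** The POTS and control groups also serve the biomarker, quality-of-life, cognitive and psychological comparisons in objectives 2 and 3 (section 2.1), which 3.3 does not size. That could be a good reason for 34. The protocol does not give it, however, so it does not support 34 as derived from 15 and 20%.

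**The authors need not have assumed a 55% loss.** A reader might infer that they did. That figure is only the algebraic equivalent of 20/9. The alternative reading of 60/0.9 shows that the base size or the loss rate could be the faulty element, so the document does not establish that 19 is the number the authors intended.

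**The burden of over-enrolment is limited.** Of the 68 − 38 = 30 participants beyond what the assumptions give, 15 are controls, and the recruitment notices seek controls who take no regular medication (the flyer excepts the contraceptive pill). At most 15 POTS patients are concerned, and only those on a listed drug.

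**The LCS precision is not shown to fail.** A reader might carry the 20% across and conclude that the 5-point target is missed. The 20% is stated only for the POTS-versus-control comparison, the LCS paragraph makes its own allowance, and cohorts may reasonably differ. The prevalence endpoint comes from a 10-minute stand on one testing day, so about 7% is not shown to be too low.

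**Conclusion.** The point holds for the POTS and control groups. The stated 15 per group and 20% loss give 19 per group (38 in total), against 34 (68 in total) described as required. This takes the document's SDs, difference, alpha and test at face value and uses the usual division by the retained fraction; the looser convention gives 18 and changes nothing.

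Severity is should-fix. A stated sample size is wrong as derived and carries into the planned total, but it enlarges a secondary comparison (about 97% power after a 20% loss) and leaves the primary estimate untouched.

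It would go too far to say that 34 per group must be cut: it may be justified on other grounds not stated. It would also go too far to say that the LCS number is wrong: 139 to 150 is arithmetically sound for about 7.3% withdrawal. What remains there is that no rate is given and the implied one differs from 20% without explanation. If 20% did apply, the half-width at 10% prevalence would be about 5.4 points instead of 5, a modest change.

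**What to change.** In section 3.3, reconcile the base size, the loss rate and the factor, in one of two ways:

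1. If 15 per group and 20% loss are what was meant, replace the 20/9 step with 30/0.8 = 37.5 and state 19 per group (38 in total). The total in section 2.5 then becomes 150 + 19 + 19 = 188.
2. If 34 per group is kept, stop presenting it as the result of 15 and 20%. Give the actual reason (for example, the biomarker and quality-of-life comparisons) and state what it delivers: about 27 evaluable per group after a 20% loss, with about 97% power for 19 bpm. If the intended inputs were different, such as 30 per group with a 10% loss, state those and their basis.

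As a secondary change, add the withdrawal rate assumed for LCS (150 allows for about 7.3%) and one sentence on why it differs from the 20% used for the other groups.

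The cost is a few sentences in 3.3 and, under option 1 only, a revised total in 2.5 and matching POTS and control numbers wherever they are given. No extra enrolment is needed.
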